## 4.2 Study Outcome Measures

### 4.2.1 Primary Outcome Measures

*Outcome 1:* SUD response to quetiapine for primary substance of use will be assessed by Timeline Followback of Substance Use to assess self-report of substance use, toxicology screens negative for substances for objective measurement of substance use, and the Weiss drug craving scale to assess cravings. The Timeline Followback will be used to compare self-report of substance for the month prior to study entry versus the last month of the study. Toxicology screens and the Weiss drug craving scale will compare values from baseline to endpoint.

*Outcome 2:* SMD response to quetiapine will be assessed by the YMRS and BDI-II comparing values from baseline to endpoint.

*Outcome 3:* The impact of treatment with quetiapine on outpatient treatment engagement will be monitored by collateral from the outpatient program regarding the percentage of scheduled appointments attended after randomization.

Outcome 4: An EKG will be administered at study screening to screen for cardiac risk factors that would exclude subjects from participation. A blood draw will be completed at screening and completion; approximately 30 ccs of blood will be drawn from each subject over the course of the study. Safety and tolerability of quetiapine monotherapy will be monitored by a battery of blood tests, weight measurements (to calculate Body Mass Index (BMI)), and the AIMS at baseline and endpoint to monitor for extrapyramidal symptoms. Weight, the AIMS, and urine HCG test will also be completed at midpoint. Adverse events, suicidality (C-SSRS), the CGI-S and CGI-I for SUD and SMD will be monitored at every study visit. Vital signs will be monitored at screening, midpoint and endpoint.

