Before receiving study medication, the healthy lifestyle behavior recommendations developed by Correll and Carlson to prevent and minimize weight gain on SGAs will be reviewed with all eligible subjects. Participating youth with active SUD and SMD will be randomized to treatment or placebo in a 1:1 ratio. Randomization lists will be generated by the investigational pharmacy for each age block (e.g. 15-17; 18-24 years). Throughout the 10-week study participants will be encouraged to engage in treatment as usual which includes evidence based behavioral therapies through the Center for Addiction Treatment for Adolescents/ Young Adults who use Substances (CATALYST) at Boston Medical Center.

Subjects will be sent appointment reminders via text before their study visits. Reminders will be sent from a cell phone designated for this study's purposes and will only contain the date, time, and location of the appointment. No personal/health information will be shared over text.

The collection of certain scales and study procedures will occur at all 11 visits, and include the following:

Clinician rated assessments:

- Mini-International Neuropsychiatric Interview (M.I.N.I. 7.0)[57]: The M.I.N.I is a short, structured, diagnostic interview with an administration time of approximately 15 minutes that is the structured interview of choice for psychiatric outcome tracking in clinical psychopharmacology trials. Specific, predetermined modules will be completed to assess for DSM-V mood disorders, disruptive disorders, SUDs and anxiety disorders (will be administered at screening). The suicidality, lifetime panic disorder and optional assessment measures to track changes over time including cross cutting measures and disability/functional impairment will not be utilized in the study. The M.I.N.I KID will be administered in subjects under the age of 18. In these interviews the suicidality, separation anxiety disorder, Tourette's disorder, adjustment disorder and autism spectrum disorder modules will also not be utilized in the study.

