- DMS-V Kiddie Schedule for Affective Disorders and Schizophrenia Present and Lifetime (KSADS-PL) module for DMDD[58]: The KSADS-PL is a semi-structured assessment of current and lifetime psychopathology in children under 18. The DMDD module has been selected to supplement clinician assessment of children under 18 who have not been diagnosed with bipolar disorder. The assessment is composed of 2 items, rated using a 0 – 3 point scale, and will take approximately 10 minutes to administer.
- Weiss Adherence Interview[59]: will be completed at the screening visit to assess patterns of medication adherence and past reason for nonadherence prior to subject enrollment (will be collected at screening).
- Adverse Experiences and Concomitant Medications: (will be collected at all study visits).
- Young Mania Rating Scale (YMRS)[60]: The YMRS is composed of 11 items, and each question is rated with a likert rating scale. It is designed to capture symptoms over the prior 48 hours, with total scores ranging from 0 to 60: (will be completed at screening, baseline, and every 2 weeks thereafter).
- Abnormal Involuntary Movement Scale (AIMS)[61]: The AIMS is used to record the occurrence of tardive dyskinesia (TD) in patients receiving neuroleptic medications. It is a 12-item anchored scale that requires raters to assess for movement in the face, lips, jaw, tongue, upper extremities, lower extremities, and trunk (it will be administered at screening, midpoint and final study visit).
- Clinical Global Impressions (CGI)[62] scale for SUD and SMD. The CGI is a measure of illness severity, improvement, and efficacy of treatment (will be collected at all study visits).
- Columbia Suicide Severity Rating Scale (C-SSRS)[63]: The C-SSRS is a suicidal ideation rating scale used to evaluate and monitor suicidality. It rates an individual's degree of suicidality on a continuum ranging from passive suicidal ideation to active suicidal ideation with specific intent and plan (will be administered at all study visits).
- DSM-V Global Assessment of Functioning (GAF) scale: The GAF will assess global functioning using a scale from 1 (worst) to 100 (best); (this will take place at the baseline, midpoint, and the final study visits).

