### 12.3 Statistical Methods

All analyses will be modified intention to treat, which will be defined by completing at least one week of study medication. We will analyze group differences across demographics using Pearson's Chi Squared tests for binary outcomes and student t tests or linear regression models for continuous outcomes. To assess our main outcomes, we will use generalized estimating equations that estimate the main effects of drug and time as well as any interactions (time X drug). We will evaluate our primary outcome measures hierarchically in the following order for SUD: Timeline Followback of substance use, urine drug screen, and Weiss craving scale. For binary outcomes, logistic regression models will be fit with Poisson family and log link, and for normally distributed data, linear regression models will be fit with the Gaussian distribution and the identity link. Exploratory aims will be examined using models similar to the main outcomes. All statistical tests will be performed using STATA 13.0. The statistical significance will be set at 5% and all tests will be two-tailed.

To evaluate hypotheses 1A, 1B and 1C, we will monitor SUD response to quetiapine for primary substance of use by way of the Timeline Followback of Substance Use (TLFB). Specifically, the TLFB will be used to compare self-report of substance for the month prior to study entry versus the last month of the study. We will use weekly toxicology screens negative for primary substance of abuse as an objective measurement of decrease in substance use severity. The Weiss Craving Scale will be used to assess the effect of quetiapine treatment on cravings for primary substance of use. Values for all three measures (TLFB, toxicology screens, and Weiss Craving Scale) will be compared between baseline and endpoint.

To evaluate hypotheses 2A and 2B, we will assess SMD response to quetiapine by way of comparing

values from baseline to endpoint on the YMRS and BDI-II.

To evaluate hypothesis 3A, the impact of treatment with quetiapine on outpatient treatment engagement will be monitored by collateral from the outpatient program regarding the percentage of scheduled appointments attended after randomization.

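### The main-outcome model in section 12.3 adjusts for neither the baseline value nor the randomisation age block: a valid test that gives up some precision at no saving

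*Combined protocol and SAP*

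**What the plan says.** Section 12.3 gives one model for the main outcomes: "we will use generalized estimating equations that estimate the main effects of drug and time as well as any interactions (time X drug"). No other term is named. The only other regression in that section is for group differences in demographics.

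Baseline appears as a time point. For TLFB, "the TLFB will be used to compare self-report of substance for the month prior to study entry versus the last month of the study". TLFB, toxicology and craving values "will be compared between baseline and endpoint". Section 4.2.1 agrees: "Toxicology screens and the Weiss drug craving scale will compare values from baseline to endpoint", and "SMD response to quetiapine will be assessed by the YMRS and BDI-II comparing values from baseline to endpoint". The SUD measures are ranked ("We will evaluate our primary outcome measures hierarchically in the following order for SUD"): TLFB first, urine drug screen second, craving third.

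Section 9.3 states: "Randomization lists will be generated by the investigational pharmacy for each age block", with 15-17 and 18-24 years given as an example, at 1:1 allocation. It also sets the visits. The YMRS "will be completed at screening, baseline, and every 2 weeks thereafter", and the BDI-II and Weiss Craving Scale follow the same two-weekly pattern from baseline. Hypothesis 3A uses the percentage of appointments attended after randomisation, so it has no baseline value.

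**The concern.** With baseline as a time level, the time-by-drug term compares change from baseline between arms. In large samples that contrast is never more precise than one adjusting for the baseline value. Section 12.2 needs only 22 analysed subjects per arm, and its effect size comes from a preliminary report on a different comparison and from a lithium trial. If the true effect is below plan, precision matters. Section 3.1 reports 161 phone screens and 19 subjects randomised before the site move, so precision is cheaper to find in the analysis than in recruitment.

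Age block raises a related question. A factor used to allocate treatment is normally kept in the model, because a test that omits it can be conservative.

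**Working it through.** **Inputs from section 12.2.** Two-sided 5%, 90% power, effect size about 1.0, 22 per group for substance use, 10 per group for mood, 20% attrition, 28 per group.

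**Reproducing the plan.** n = 2(1.960 + 1.282)²/1.0² = 21.01, rounded up to 22 per group. By the t-test, power at 22 per group is 89.97%. 22/0.8 = 27.5, rounded up to 28 per group and 56 in total. The planned size therefore matches an effect of 1.0 SD. The text does not say whether that SD is of the endpoint value or of the change.

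**Assumptions not in the documents.** r = 0.3, 0.5 and 0.7; equal SDs at baseline and endpoint unless stated; complete data; 22 per arm.

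**Variance per subject, in units of endpoint SD².** Change: 2(1-r) = 1.40/1.00/0.60. Baseline-adjusted: 1-r² = 0.91/0.75/0.51. Ratio: (1+r)/2 = 0.65/0.75/0.85. With unequal SDs the difference is (baseline SD - r × endpoint SD)², which cannot be negative.

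**Power.** Change figures are from the noncentral t. Adjusted figures are from simulated ANCOVA with baseline and a non-predictive age block (40 df).

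| Effect | Change, r = 0.3/0.5/0.7 | Adjusted |
|---|---|---|
| 1.0 endpoint SD | 78/90/99% | 92/96/99% |
| 0.7 endpoint SD | 48/62/83% | 65/74/88% |
| 1.0 change SD | 90/90/90% | 98/96/93% |

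A five-visit Gaussian GEE with exchangeable working correlation and robust standard errors gives the same picture: 79/90/99% against 92/96/100% at 1.0 endpoint SD.

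Subjects per arm for 90% power at 1.0 endpoint SD, by noncentral t without the small loss for estimating the covariates: change 31/23/14, adjusted 21/17/12.

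**TLFB.** Entry requires use on at least half of the past 28 days (section 7.1), which may narrow baseline spread. If baseline SD is 0.6 of endpoint SD (assumed), the change variance is 1 + 0.36 - 1.2r = 1.00/0.76/0.52 against 0.91/0.75/0.51 adjusted. The power difference runs from -0.7 to +2.7 points over effects of 0.7 and 1.0.

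**Mood.** Ten per group at 90% power implies an effect of 1.53 SD by the t-test. With 22 per arm, both analyses then have at least 98.7% power.

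**Age block.** Simulation of 44 subjects, about 30% in the younger block, with an age effect of 1 SD on the change (assumed). Unadjusted type I error is about 3% if allocation is balanced within blocks, and about 5% if it is not. If the age effect is constant over time, it cancels from the change and type I error is again about 5%.

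**Cost.** At an effect of 0.7 SD and r = 0, endpoint-only power of 62.1% falls to 60.8% when both covariates are added.

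Power was not computed for toxicology or 3A.

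**The case against.** The strongest reply is that nothing here is wrong. Change from baseline is a valid comparison under randomisation, and the results quoted in section 12.2 are improvements from baseline (joints per week from 14 to 4, YMRS down by 16). It is therefore natural to read the effect of about 1.0 on the change scale, where the plan has its 90% at every r. The 78% figure needs an endpoint-scale effect and r = 0.3, and the 48% figure needs a smaller effect as well. The gain is also smallest for TLFB, which is first in the SUD order. All of this stands, and it limits the point to precision.

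Three stronger readings are tempting, and the documents support none of them.

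- A reader might infer that the trial is underpowered. That depends on r and on the SD scale, and neither is given.
- A reader might infer that omitting the age block distorts the test. Conservatism needs both balance within blocks and an age effect on change. Section 9.3 mentions lists per block but no permuted blocks or block size, and nothing in the documents indicates that age predicts change.
- A reader might infer that an unnamed contrast (Week 8 or slope) inflates type I error. Sections 4.2.1 and 12.3 favour endpoint minus baseline, and nowhere is it proposed to accept either test. Naming the contrast is a clarification.

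One practical objection also stands. The modified intention-to-treat set requires one week of medication, but craving, YMRS and BDI-II are first repeated at Week 2. A model of post-baseline values alone would drop a subject who leaves in between. The fix allows for this.

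**Conclusion.** The omission is real: no section puts the baseline value or the age block into the main-outcome model. The planned test remains valid, so this is a cheap precision improvement and not a correction of an error. Under equal SDs and r from 0.3 to 0.7, adjustment removes 35% to 15% of the variance. At the planned size that is worth about 14 power points at r = 0.3 and almost nothing at r = 0.7 if the effect is 1.0 endpoint SD, or about 8 to 3 points if it is 1.0 change SD. The benefit falls mainly on craving, or on any of these outcomes whose effect is below plan. It is near nil for mood at the planned effect, and for TLFB if baseline spread is narrow. The case for including age block is consistency with the allocation; a measurable gain depends on two conditions that the documents do not establish. The sizes rest on assumed r, assumed SD ratios and complete data, although section 12.2 expects 20% attrition.

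**What to change.** Amend section 12.3 before unblinding:

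- **Craving, YMRS, BDI-II:** model drug, visit, drug-by-visit, baseline value and age block, with the Week 8 drug-versus-placebo contrast as the test. To keep modified intention-to-treat subjects who have no post-baseline value, an equivalent is to retain baseline as a visit and constrain its mean to be equal across arms.
- **TLFB:** model the last-month value on drug, prior-month value and age block, with the drug contrast as the test.
- **Toxicology:** keep the stated comparison and planned model; add age block only.
- **Hypothesis 3A:** compare arms on percentage attended, adjusting for age block only.

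State the age blocks actually used, since section 9.3 gives them as an example. The change needs no new data. It uses about two degrees of freedom per model with both covariates, roughly one power point if neither predicts outcome.

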### 13 Ethics/Protection of Human Subjects

This study is to be conducted according to applicable US federal regulations and institutional policies (which are based in federal regulations, guidance, and ICH Good Clinical Practice guidelines).

This protocol and any amendments will be submitted to the Boston Medical Center and Boston University Medical Campus IRB, for formal approval of the study conduct. The decision of the IRB concerning the conduct of the study will be made in writing to the investigator

All subjects for this study will be provided a consent form describing this study and providing sufficient information for subjects to make an informed decision about their participation in this study. The consent form will be submitted with the protocol for review and approval by the IRB. The consent of a subject, using the IRB-approved consent form, must be obtained before that subject is submitted to any study procedure. Consent will be documented as required by the IRB.

## 15 Appendix

1. Schedule of Events
2. DSMB Charter
3. Case Report Forms (CRFs)
  - a. Urine Drug and Breathalyzer
  - b. Adverse Events
  - c. CBCL
  - d. MARS
  - e. AIMS
  - f. BDI-II
  - g. Craving Scale
  - h. ABCL
  - i. Concomitant Medications
  - j. Reproductive Potential
  - k. Fagerstrom Tolerance Questionnaire
  - l. Chart Notes (Week 98 & 99, Week 0, Weeks 1-8)
  - m. KSADS DMDD Module
  - n. Electronic Cigarette Use Questionnaire
  - o. GAF
  - p. Supplemental Substance Use Questionnaire
  - q. BRIEF-Subscale Adult
  - r. BRIEF- Subscale Parent
  - s. BRIEF- Subscale Informant
  - t. BRIEF-Subscale Self-Report
  - u. Demographics Facepage
  - v. Lifetime Weiss Adherence Interview
  - w. ASR
  - x. CSSR-S
  - y. YSR
  - z. CGI SMD
  - aa. YMRS
  - bb. PHQ9
  - cc. Risk Behavior Survey
  - dd. MINI Adult 7.0
  - ee. MINI Kid 7.0
  - ff. CGI SUD
  - gg. Timeline Followback Forms (2020, 2021)
  - hh. COVID-19 Screening Questions
4. Data Management Plan
5. Informed Consent
6. Recruitment Flyer
7. Medication Diary
8. Deviation Exception Log

9. Healthy Lifestyle Behaviors
10. Dosing Instructions
11. Recruitment Email
12. Telephone Script
13. Quetiapine package insert
